3.3. Hypotheses

[figure not shown]
- A) Exposure to the intervention will be associated with significantly lower mean burnout severity by comparison to a waitlist (delayed intervention) control group
- B) After the control group is exposed to the intervention, there will be no significant differences in mean burnout level between the two groups (immediate intervention group, delayed intervention group)
- C) Mean burnout severity for all participants at the end of the 6-month follow-up period will be significantly lower than baseline severity (prior to intervention), but not significantly different to endof-treatment severity, indicating maintenance of gains

4. Study design

This will be a pragmatic, stepped wedge, open-label, randomised controlled trial. Consenting doctors will be randomly assigned to two groups, by a research assistant using a computerized randomization algorithm. The randomisation sequence will be based on random blocks of 10 participants, and

stratification according to participants' employing organisation (trial site). The study will be carried out in three phases, which are illustrated in Figure 1.

Figure 1. Stepped wedge trial design

Participants in both groups will be asked to complete outcome measures during a pre-intervention baseline assessment (week 0). After the baseline assessment, only participants in group 1 will access an 8 session, 10-week intervention (controlled phase). Next, group 2 will access the intervention during a 10-week period (full implementation phase). Finally, we will collect further outcome measures 6 months after both groups have completed the intervention (follow-up phase). Selected outcome measures (see section '4.3 Measures' for more details) will be completed at each of the measurement points outlined in the above timeline (weeks 0, 10, 20, 44). All measures will be completed online using an industry-standard survey system (Qualtrics), which will be managed by a research assistant.

The end of the study is classed as once the participant has completed the six-month follow-up questionnaire. However, the participants email addresses will be kept for up to six months after this to ensure the research team can disseminate the results of the study. Following this, all personal data will be deleted.

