Participants who do not attend at least one intervention session will be classed as part of a 'non-intervention' group. The baseline data for these participants will be retained and, unless they have formally withdrawn, they will be invited to complete the questionnaires at each of the above timepoints so we can include their outcome measures in the primary data analysis, following intention-to-treat principles (see section 5.2).

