- After Group 1 has completed the ten-week, eight session intervention, the second group will have access to the same intervention using the process outlined above in Figure 1.

Data collection and safeguarding procedures

All participants irrespective of group allocation will be asked to complete the primary and secondary
measures described above, at four assessment points, as described in the 'Measures' section above.
 The measures will be collected by an independent NHS-based research team, who is not involved

directly in the intervention delivery. The researchers will use a secure, web-based, data collection system called Qualtrics.

- The consent and demographic questionnaires will ask for the participant's preferred email address. This is to ensure we are able to contact the participants throughout the study period (e.g., sending email reminders). Once they have completed the consent form we will email the participants a unique participant pseudonym, which cannot personally identify any of the study participants. The participant will then use this pseudonym to identify themselves throughout the rest of the study (i.e., to log in to the Microsoft Teams webinar). The research team will keep a record of the participant's email address and associated pseudonym, so if the participant forgets their code they can contact the team to retrieve these details. Staff in the research team will schedule the MS Teams sessions and will invite participants using their email addresses (this is required for the breakout session facility to be used). All participants' email addresses will be deleted after 2 years, which is a time-scale that we expect will allow sufficient time for the study to be concluded and to enable the research team to communicate all of the relevant results to participants via email.
- The measures will be collected by the research team using a secure, web-based, industry-standard data collection system. Therefore, all data collection will be in electronic form. Participants will receive email reminders (sent confidentially by the research team) at the relevant measurement points (see Figure 1). A maximum of 3 reminder emails will be sent to non-responding participants at each of the measurement points. If participants do not respond after the 3 reminders, we will consider that specific data-point to be missing. To access the survey, each participant will click on the link to access the survey via Qualtrics.

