5.2. Primary analysis

Trial data will be summarised using a CONSORT diagram and all analyses will be based on *intention-to-treat* principles (e.g., including all available data for participants who never attended intervention sessions, those who attended all sessions, and those who dropped out after a few sessions). Intention-to-treat principles will be followed to minimise well-known biases present in "completer analysis" (e.g., only including data from those who complete the intervention, who may not be representative of the wider population of eligible participants in need for treatment) and to follow best practice principles in healthcare research (White et al., 2011). Missing data will be imputed using an expectation-maximization algorithm, prior to conducting formal analyses.

The primary hypothesis test will be based on comparing mean OLBI (total severity) scores between groups at week 10 (post-intervention), as shown in Figure 1. Mean OLBI scores (dependent variable) will be compared between groups using ANCOVA, adjusting for baseline severity and entering "intervention group" as an independent variable. Adjusted 95% confidence intervals will be calculated around the adjusted mean difference between interventions. The analysis will be conducted using the Statistical Package for the Social Sciences (SPSS) by a researcher who will be blind to the label of the interventions. The primary analysis will be conducted using imputed data, following intention-to-treat principles. Secondary analyses will repeat the above ANCOVA model using per protocol analysis (only including participants that actually started the intervention; and excluding data from those in the 'non-intervention' group) and an unimputed dataset (e.g., completers analysis), to test the robustness and stability of the main analysis.

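### The week-10 per-protocol ANCOVA selects Group 2 on attendance that occurs after its week-10 outcome, so it can be biased as a robustness check

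*Protocol*

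**What the plan says.** Section 5.2 makes the primary analysis an ANCOVA of total OLBI at week 10, adjusted for baseline, on all randomised participants with imputation. It then adds: "Secondary analyses will repeat the above ANCOVA model using per protocol analysis", with the population given as "only including participants that actually started the intervention" and the non-intervention group left out. The stated purpose of this and the unimputed analysis is to check how robust and stable the main result is.

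The excluded group is defined in Section 4: "Participants who do not attend at least one intervention session will be classed as part of a" non-intervention group. That definition has no time limit and no separate rule for Group 2 at week 10.

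Section 4 gives only Group 1 access between baseline and week 10. Section 4.4 confirms the order: "After Group 1 has completed the ten-week, eight session intervention, the second group will have access to the same intervention".

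Section 5.3 repeats the Section 5.2 analysis at week 44. It also applies it to the OLBI subscales, WEMWBS and job satisfaction at weeks 10 and 44.

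**The concern.** A per-protocol comparison is informative only if the rule for staying in it means the same thing in both arms. Here it does not. A Group 1 doctor qualifies by attending in weeks 0-10, before the week-10 outcome. A Group 2 doctor can qualify only by attending after week 10, when that outcome has already been recorded. A doctor's burnout at week 10 may influence whether they take up the sessions then on offer. If so, the outcome partly decides who counts as a control.

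At stake is the interpretation of the primary result. A check of this kind can appear to confirm or to contradict the main analysis through selection alone, and a reader could not tell which had happened. The exclusion is also not marginal: the synopsis expects roughly 120 non-intervention participants beyond the 180 target.

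**Working it through.** **1. The plan's own figures.** Inputs from Section 5.1: f = 0.30 (d = 0.6), alpha 0.05, power 80%, two groups, one covariate. The power of the F-test uses 1 and N − 3 degrees of freedom and noncentrality f²N. N = 89 gives 0.799 and N = 90 gives 0.804, so the minimum is 90. Attrition: 90 / (1 − 0.5) = 180. Both stated figures reproduce, and this point does not touch them.

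**2. The rule set against the timeline.**

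| | Group 1 | Group 2 |
|---|---|---|
| Can attend | weeks 0-10 | after week 10 |
| Outcome in the repeated model | week 10 | week 10 |
| Attendance that decides inclusion (whole-trial definition) | before the outcome | after the outcome |
| Starters if judged at week 10 | those who attended | none |

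The whole-trial reading is the likelier intent, because Section 4 defines the non-intervention group without a cut-off.

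**3. Share excluded.** If the 120 are additional to the 180, as the synopsis words it, the share is 120 / (180 + 120) = 40%.

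**4. Size of the possible bias.** The documents give no figure for how uptake depends on burnout, so what follows is an assumed range. Set-up:
- no true effect, equal arms, and a baseline to week-10 correlation of 0.6 (assumed);
- 60% start in each arm;
- the log-odds of starting are linear in the baseline score for Group 1 and in the week-10 score for Group 2;
- ANCOVA on starters only, two-sided 5% test, several thousand simulated trials per setting.

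| Odds ratio of starting per SD of burnout | False difference (SD) | Type I error, 300 randomised | Type I error, 180 randomised |
|---|---|---|---|
| 1.0 | 0 | 5% | 5% |
| 1.1 | 0.02 | 5% | 6% |
| 1.2 | 0.04-0.05 | 6% | 6% |
| 1.5 | 0.10 | 13-14% | about 10% |
| 2.0 | 0.16 | 25-28% | about 18% |

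Inverse odds ratios (0.67 and 0.5) give about the same sizes with the opposite sign. If more burnt-out doctors are likelier to start, the Group 2 starters are left with high week-10 scores and the intervention looks falsely beneficial. If they are less likely to start, it looks falsely harmful.

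**5. Control run.** When starting depends on baseline in both arms, the false difference is about zero and type I error about 5%, at odds ratios of 1.5 and 2 alike. Baseline adjustment deals with that case. The bias in step 4 therefore comes from selecting Group 2 on its own outcome.

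**6. Scale.** Against the design effect of 0.6, 0.10 / 0.6 is about one-sixth and 0.16 / 0.6 about one-quarter.

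**The case against.** The best defence is that, with delayed access, later uptake in Group 2 is the only observed sign of who would have started. Restricting both arms to starters then compares like with like, provided uptake reflects stable characteristics or scheduling. The protocol does point to shift patterns (Section 4.4) and to the busy nature of healthcare work (Section 5.1). This stands as a condition: if uptake depends only on such factors or on baseline burnout, there is no bias. The protocol neither shows nor excludes dependence on week-10 burnout, and the rule offers no protection if it exists.

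It is also fair to say that every per-protocol analysis gives up randomised comparability, that this is a secondary check, and that finer rules often sit in a statistical analysis plan. The first two limit the weight of the point. The third does not answer it, because the protocol itself states the population, the model and the purpose.

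A reader might infer that the control arm is empty. That follows only if starting is judged at week 10. It is a literal reading of one clause, but the accompanying exclusion of the non-intervention group, defined over the whole trial, makes it the less likely meaning.

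Keeping all of Group 2 and dropping only Group 1 non-starters would avoid both problems. It is not what Section 5.2 says, and it would compare selected starters with an unselected control arm.

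**Conclusion.** The point holds as a defect in a stated secondary analysis. Under the likelier reading, Group 2 is filtered on attendance that follows its week-10 outcome, and Group 1 on attendance that precedes it. The result is biased if Group 2 uptake depends on week-10 burnout beyond baseline.

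Direction and size cannot be derived from the protocol. Over assumed odds ratios of 1.1 to 2, the false difference runs from negligible to about a quarter of the design effect, and type I error from nominal to about 28% with 300 randomised. At the minimum of 180 it is about 10% and 18% for odds ratios of 1.5 and 2. These figures rest on the assumed correlation of 0.6, 40% not starting and the assumed uptake model.

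A reader might go further and conclude that the trial's main result is compromised. It is not: the primary analysis keeps never-attenders in both arms, and the sample size reproduces. The change should be made, but the primary inference does not depend on it.

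**What to change.** 1. State in Section 5.2 that Group 2's attendance after week 10 never selects week-10 data, for OLBI or for the outcomes that Section 5.3 analyses in the same way.
2. At week 10, replace the starters-only ANCOVA with a complier-average causal effect by two-stage least squares. Randomised arm is the instrument for having attended at least one session by week 10 (zero for all of Group 2), adjusted for baseline OLBI as in the primary model.
3. State the exclusion restriction: assignment affects week-10 OLBI only through attendance. It deserves a comment, because the trial is open-label and Group 2 knows it is waiting.
4. Report the result as an estimate of the effect in attenders. With no Group 2 attendance before week 10 it is essentially the intention-to-treat difference divided by the proportion of Group 1 attending, so its null test adds no independent evidence.
5. Limit this estimator to week 10. By week 44 both groups have had access and the instrument no longer separates attenders from non-attenders.

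Cost: a wording change, using attendance that the trial must already record to classify participants. The downsides are one added assumption and a wider interval. With 60% of Group 1 attending, for example, the interval would be about 1 / 0.6 = 1.7 times the width of the intention-to-treat interval.

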5.3. Secondary analyses

The analysis described above will be repeated at the 44-week follow-up. In addition, these analyses will be repeated at each of the post-intervention time-points illustrated in Figure 1 (weeks 10, 44), using the OLBI sub-domain scores (*exhaustion*; *disengagement*), the WEMWBS well-being measure, and the JDSS job satisfaction measure, controlling for baseline scores. These between-group comparisons will also be summarised using effect sizes (Cohen's d).

Post-intervention measures (weeks 10, 20, 44) will be compared to baseline measures (week 0) within each group, using paired-samples t-tests or an appropriate non-parametric test depending on the distribution of the data. Within-sample pre-post treatment effect sizes will also be computed using the method proposed by Minami et al. (2008).

Dropout will be defined as attending less than 4 (half) of the intervention sessions. We will examine predictors of dropout and treatment response (defined as reliable improvement in the OLBI measure), using all available baseline measures as candidate predictors. Reliable predictors of each of these outcomes of interest will be identified using a variable selection method called Elastic Net Regularization (Zou & Hastie, 2005) applied in separate logistic regression models for each dependent variable.

Additional secondary analyses will examine variability in burnout, wellbeing and job satisfaction across groups defined by their job role and demographic characteristics. Between-group comparisons will be made using t-tests (or Mann-Whitney U Tests if the data are not normally distributed).

Qualitative data collected via online surveys after all participants had the opportunity to access the intervention (week 20) will be analysed using thematic analysis (TA). TA will follow the 6-step phase of

analysis proposed by Braun and Clarke (2006). We will triangulate qualitative themes generated via the TA method with baseline survey data in order to explore if the themes vary according to job role (e.g., junior doctors, consultants, etc.) and setting (e.g., community vs. hospital services).

6. Ethical considerations

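### Section 5.3 treats week 10 as post-intervention in both groups, so Group 2's within-group contrasts with week 0 contain the ten-week wait and cannot be read as pre-post treatment effects

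*Protocol*

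**What the plan says.** Section 5.3 gives one rule for both groups: "Post-intervention measures (weeks 10, 20, 44) will be compared to baseline measures (week 0) within each group". It uses paired t-tests or a non-parametric alternative. The next sentence adds effect sizes: "Within-sample pre-post treatment effect sizes will also be computed using the method proposed by Minami et al. (2008". No other pre-treatment point is named, and no exception is made for Group 2.

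The treatment schedule is in section 4. Baseline is common: "Participants in both groups will be asked to complete outcome measures during a pre-intervention baseline assessment (week 0". Then "After the baseline assessment, only participants in group 1 will access an 8 session, 10-week intervention (controlled phase", and "Next, group 2 will access the intervention during a 10-week period (full implementation phase". Section 4.4 confirms the order: "After Group 1 has completed the ten-week, eight session intervention, the second group will have access to the same intervention". Hypothesis A in section 3.3 describes the comparison arm in these terms: "significantly lower mean burnout severity by comparison to a waitlist (delayed intervention) control group". Outcome measures "will be completed at each of the measurement points outlined in the above timeline (weeks 0, 10, 20, 44", so Group 2 has a scheduled score at week 10.

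**The concern.** The two sections cannot both describe Group 2 at week 10. In the primary analysis (section 5.2) that score is the untreated control value. In the within-group analysis of section 5.3 the same score is listed as a post-intervention measure. The label fits Group 1's calendar and has been carried over to Group 2.

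If the rule is followed as written, the report would present a Group 2 baseline-to-post-intervention change at week 10 during which nobody in that group had access to the intervention. It would also present Group 2 changes at weeks 20 and 44 in which natural change, regression to the mean or anticipation during the wait is counted with the effect of the programme. A pre-post treatment effect size built on these contrasts would not measure what its name says. At end of treatment it would span 20 weeks in Group 2 against 10 in Group 1.

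**Working it through.** **Inputs.** Comparison rule: section 5.3. Treatment windows: Group 1 weeks 0 to 10, Group 2 weeks 10 to 20 (sections 4 and 4.4). Measurement points: weeks 0, 10, 20 and 44 (section 4). Expected waiting-list change: not given anywhere.

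**The plan's own figure.** The protocol gives no number for this point. Its only computed figure is the sample size in section 5.1, which reproduces: with f = 0.30, alpha 0.05, two groups and one covariate, the noncentral F distribution gives a total of 90 with power 0.804, and 90 / (1 - 0.5) = 180. Nothing below changes it.

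**Step 1: set the rule against the schedule.**

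| Contrast with week 0 | Group 1 | Group 2 |
|---|---|---|
| Week 10 | 10 treated weeks | 10 waiting weeks, 0 treated |
| Week 20 | 10 treated + 10 after | 10 waiting + 10 treated |
| Week 44 | 10 treated + 34 after | 10 waiting + 10 treated + 24 after |

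Every Group 2 contrast contains the wait, and the week-10 contrast contains nothing else.

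**Step 2: decompose the Group 2 contrasts.** Let Y(t) be Group 2's mean at week t, and let w = Y(10) - Y(0) be the waiting-list change.

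- Weeks 0 to 10: Y(10) - Y(0) = w
- Weeks 0 to 20: Y(20) - Y(0) = w + [Y(20) - Y(10)]
- Weeks 0 to 44: Y(44) - Y(0) = w + [Y(44) - Y(10)]

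The bracketed terms are the changes since the last pre-treatment score. As estimates of those changes, the week-0 contrasts are off by exactly w, whatever its size or sign.

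**Step 3: illustrate the size.** This step is assumption throughout. Count improvement as positive, standardise every contrast by the same SD, let w run from -0.2 to +0.2 SD, and take 0.6 SD as a placeholder for the change over weeks 10 to 20. The value 0.6 is borrowed from section 5.1, where it is a between-group effect.

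- Weeks 0 to 20: 0.6 - 0.2 = 0.4 to 0.6 + 0.2 = 0.8
- Weeks 10 to 20: 0.6 throughout
- Weeks 0 to 10: -0.2 to +0.2, with no treatment given

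The absolute shift is w and does not depend on the placeholder.

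**The case against.** The case for leaving the text alone has real content.

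- **Week 0 is the trial's common baseline.** Change from week 0 to week 20 or 44 in Group 2 is a legitimate description of total change since enrolment. This stands. The fault lies in calling Group 2's week 10 post-intervention and in reading the week-0 contrasts as treatment effects, not in computing them.
- **The waiting-list component is already computed.** The week 0 to 10 contrast in Group 2 is part of the plan, so a careful reader could see it beside the week-20 result. This also stands, but it would be reported under the wrong name, and the change from week 10 to week 20 is not planned at all.
- **Re-basing does not isolate a treatment effect.** Group 1's change over weeks 0 to 10 is uncontrolled too, and regression to the mean since enrolment may be partly spent in Group 2 by week 10. This is correct. Re-basing makes the Group 2 contrast cover the treatment period; causal evidence still comes from the randomised comparison.
- **The downstream links are inferred.** The effect-size sentence names no pre-treatment value; week 0 is taken from the sentence before it. Reliable improvement is given no time points, a detail that a statistical analysis plan may supply. Hypothesis C pools all participants, whereas section 5.3 tests within each group. A reader might infer that Hypothesis C and the treatment-response model are biased; the protocol does not fix enough to say so.
- **A percentage bias is not available.** A reader might divide an assumed waiting-list change by 0.6 and quote a share of the effect. That 0.6 is a between-group design value, not an expected pre-post change, so the ratio does not describe the quantity at issue.

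**Conclusion.** The point holds, within limits. As written, section 5.3 mislabels Group 2's last pre-treatment score and gives Group 2 no contrast that starts at treatment. This follows from the protocol's own timeline and needs no outside figure; Figure 1 is not shown, but the text of sections 4 and 4.4 fixes the order. The magnitude is unknown in size and direction; the 0.4 to 0.8 range only illustrates the assumed ±0.2 SD.

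A reader might infer that the main result is compromised. It is not: the week-10 ANCOVA in section 5.2 needs Group 2 to be untreated at week 10, and it is. The sample size is untouched as well. The defect is confined to non-randomised secondary analyses. It should be corrected there, because waiting-list change could otherwise be reported as a post-intervention effect.

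**What to change.** In section 5.3:

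1. Define pre-treatment as week 0 for Group 1 and week 10 for Group 2, and end of treatment as week 10 for Group 1 and week 20 for Group 2.
2. Compute the within-group treatment tests and effect sizes from the group's own pre-treatment point to end of treatment and to later points: Group 1 weeks 10, 20 and 44; Group 2 weeks 20 and 44.
3. Keep the contrasts with week 0, labelled as total change since enrolment, and report Group 2 weeks 0 to 10 as control-phase change.
4. If reliable improvement on the OLBI is meant to represent treatment response, take it between the same group-specific pre-treatment and end-of-treatment points.

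The end-of-treatment contrasts then cover 10 weeks in each group. The week-44 contrasts still differ in length (44 weeks from pre-treatment in Group 1; 44 - 10 = 34 in Group 2), which the report should state.

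The cost is wording: the OLBI, WEMWBS and job satisfaction scale are already collected at all four points. The downside is that Group 2's pre-treatment value becomes a post-randomisation score subject to attrition, so participants without a week-10 score depend on the expectation-maximization imputation planned in section 5.2. Keeping the week-0 contrasts alongside limits that dependence.

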5.1. Sample size calculation

Using G*Power to perform a sample size calculation for a between-groups analysis of covariance (ANCOVA), with 80% power, an alpha level of 0.05, and controlling for intake severity to detect an effect size of d=0.6 (based on the CPM 1 trial (ISRCTN34503872) - converts to f=0.30) estimates that at least 45 participants are needed in each group (total sample size of 90).

Accounting for a drop-out rate of 50% (based on the lost-to-follow-up rate at 6-month follow-up in CPM 1), would inflate the total required sample size to a minimum of 180 (90 in each group). This high dropout rate is associated with the busy nature of healthcare, which makes it difficult to retain NHS staff in clinical trials, and hence it is essential to work to a conservative sample size calculation.

For reference, CPM 1 recruited a total of 173 participants (G1=83, G2=90). So, if we were to account for the expected follow-up drop-out rate, we would need to recruit more participants than CPM 1. Therefore, to ensure that the trial is adequately powered and robust to the expected level of attrition, we propose to recruit a minimum of 180 participants and to continue to recruit as many participants as are willing to provide consent within the 3-month recruitment period. In order to ensure the trial recruits to target and is robust to attrition, we will recruit from multiple NHS service providers across England.

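### On its natural reading, the protocol derives OLBI treatment response from EM-filled scores; if these are expected values, many responders are misclassified and the response predictors distorted

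*Protocol*

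**What the plan says.** Protocol section 5.2 (Primary analysis) bases all analyses on intention-to-treat principles and states: "Missing data will be imputed using an expectation-maximization algorithm, prior to conducting formal analyses". The unimputed dataset appears only as a robustness check on the ANCOVA: "Secondary analyses will repeat the above ANCOVA model using per protocol analysis", followed by the same model on unimputed data.

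Section 5.3 (Secondary analyses) then states: "We will examine predictors of dropout and treatment response (defined as reliable improvement in the OLBI measure), using all available baseline measures as candidate predictors". Response is modelled by elastic net within a logistic regression, so it is a yes/no classification of each person's OLBI change. The section gives no missing-data rule, cut-off or time point for response.

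The expected loss is in section 5.1: "Accounting for a drop-out rate of 50% (based on the lost-to-follow-up rate at 6-month follow-up in CPM 1". Section 4.3 gives Cronbach's alpha of .74 to .76 for each OLBI subscale and none for the total score.

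**The concern.** An EM fill, in its plain form, is the expected score given the observed data. It carries no individual residual, so filled changes vary much less between people than real changes do. Applying a cut-off to an expected change does not give the expected response.

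Among people who did not return the survey, response is then settled almost entirely by the variables used in the imputation. If those include the baseline measures, the elastic net partly recovers the imputation rule. A baseline variable that predicts only survey non-return can also pass for a predictor of non-response, because non-returners are mostly coded as non-responders. The planned unimputed analysis would not reveal this, since it repeats only the ANCOVA. At stake is the secondary objective on predictors of treatment response.

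**Working it through.** **The protocol's own figures.** The calculation runs "with 80% power, an alpha level of 0.05, and controlling for intake severity to detect an effect size of d=0.6", which "converts to f=0.30" (f = d/2). For a two-group ANCOVA with one covariate, the noncentrality is f²N = 0.09 × 90 = 8.1. Power is 0.804 at N = 90 and 0.799 at N = 89, so "at least 45 participants are needed in each group (total sample size of 90" reproduces. 90/(1 − 0.5) = 180 also reproduces. The protocol gives no response rate or misclassification figure to compare with.

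**Model (assumed).** Work in baseline SD units. Baseline b is N(0,1). Follow-up is y = ρb − m + residual, with residual variance 1 − ρ². Response means b − y ≥ c, where c = 1.96 × √(2(1 − reliability)). The EM fill from baseline alone is ρb − m.

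**Inputs.** Half the scores are missing (the 6-month figure in 5.1). Reliability 0.85 for the total score, ρ = 0.6 and m = 0.6 SD are assumptions. The value of m borrows the size of the protocol's between-group d and is not a documented within-person change.

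**One scenario by hand.**
- Cut-off: c = 1.96 × √0.30 = 1.0735.
- True response: the SD of change is √(2(1 − 0.6)) = 0.894. P = 1 − Φ((1.0735 − 0.6)/0.894) = 29.8%.
- Filled response: the filled change is 0.6 + 0.4b, with SD 0.4. P = 1 − Φ((1.0735 − 0.6)/0.4) = 11.8%.
- Overall: 0.5 × 29.8% + 0.5 × 11.8% = 20.8%.
- Among non-returners, response reduces to a rule on baseline: b ≥ 0.4735/0.4 = 1.18.
- By simulation, about 76% of true responders among non-returners are scored as non-responders.

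**Range.** Over 44 scenarios (reliability 0.76 to 0.90, ρ 0.5 to 0.8, m 0 to 0.9 SD), the missed share runs from 32% to 100%. It exceeds half in 39. The five exceptions all have m = 0.9 SD. At m = 0.6 SD it is 53% to 98%. At m = 0.9 SD, reliability 0.90 and ρ = 0.6, the filled rate is slightly above the true one (52.4% against 51.0%).

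**Effect on predictors** (reliability 0.85, ρ = 0.6, m = 0.6 SD, 50% missing, plus a weak second predictor explaining 5% of residual variance; unpenalised logistic regression):

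| | True | EM expected value | EM with residual drawn |
|---|---|---|---|
| Response rate | 29.8% | 21.8% | 29.9% |
| Odds ratio, baseline OLBI per SD | 2.36 | 4.11 | 2.36 |
| Odds ratio, second predictor | 1.48 | 1.91 | 1.49 |

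With 30% missing, the baseline OLBI odds ratio is 3.10 instead of 2.36. Both odds ratios were inflated in all 13 simulated datasets of this kind, baseline OLBI by about 1.3 to 2.1 times. This is not universal. In a rerun at ρ = 0.7 and m = 0.3 SD, almost no filled record crosses the cut-off, and the baseline odds ratio barely moves although about 98% of true responders are missed.

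**A variable that predicts only non-return.** Give a baseline variable no effect on OLBI but a strong effect on survey return, with about half the scores missing. Its true odds ratio for response is 1.00. After the fill it is about 0.63 to 0.75 per SD at improvements of 0.3 to 0.6 SD. A rerun of the main scenario, with the log-odds of non-return rising by 1 per SD, gave about 0.75. A weaker link moves it nearer 1.00. Residual draws or observed records return 1.00.

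**The case against.** The strongest objection is that the error is inferred. The EM sentence sits under the primary analysis, and only the primary analysis is named outright as using imputed data. Nothing says that response is cut from filled scores, or that the fills lack residuals. This stands as a limit on certainty. Even so, an intention-to-treat rule for all analyses, with imputation before formal analyses, makes it the natural reading. A statistical analysis plan, not available here, might settle it.

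A reader might infer that most true responders among non-returners are always lost, that the response rate is always understated, or that baseline OLBI separates filled responders perfectly. The documents support none of these. They give no total-score reliability, pre-post correlation or within-person change, and the missed share falls below half under a large improvement. It also falls to 41% to 51% if another baseline variable explains 40% of the residual variance (reliability 0.85, ρ 0.5 to 0.7). Perfect separation needs a fill from baseline OLBI alone, whereas the protocol also collects OLBI at weeks 10 and 20. With one observed intermediate wave correlating 0.6 to 0.8 with the outcome, and the main scenario otherwise, the missed share is 42% to 64% and the filled rate 17% to 24%. The error shrinks but remains, and only people with such a score benefit.

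Three further points stand. The 50% is a 6-month loss, and the time point for response is not given. Section 5.3 plans no response rate as an output, so the distortion of the predictors matters more than the rate. Using observed pairs alone as the main analysis would discard about half the records at that loss and sit badly with the protocol's own objection to completer analysis.

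**Conclusion.** The point holds, conditionally. If response is derived from expected-value EM fills, as sections 5.2 and 5.3 naturally read, it is misclassified among non-returners and the predictor model is distorted. In the main scenario about 76% of true responders among non-returners are missed, the response rate drops by about 9 points (29.8% to 20.8%), and the baseline OLBI odds ratio rises from about 2.3 to 4.1. The missed share is about a third or more across the other baseline-only assumptions tried, apart from strong auxiliary information, which also reduces the error. The rate is usually, not always, too low. A variable linked only to survey return can look like a predictor of non-response.

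These sizes rest on bivariate normality, scores missing at random and the assumed inputs above, and they shrink if fewer scores are missing. The problem is confined to an exploratory secondary objective and does not touch the primary week-10 comparison.

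**What to change.** In section 5.3, state that treatment response is not derived from expected-value EM fills. Derive it within each of several imputed datasets that draw residual variation, and fit the elastic net across them with a stated rule for combining variable selection. Add a sensitivity analysis restricted to people with both an observed baseline and an observed post-treatment OLBI, and report the proportion of response statuses that were observed.

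The cost is a few sentences and modest extra programming to combine variable selection across imputations. No new data are needed. The observed-pairs analysis uses fewer records, about half at the expected 6-month loss, which is why it belongs as a check and not as the main analysis.
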